#### **4.3 Discontinuation from Trial Treatment**

The following events may be considered sufficient reason for discontinuing treatment with the study medication:

- NCI CTCAE v5.0 Grade 3/4 non-hematological toxicity related to study drug that necessitate withdrawal in the opinion of investigator.
- Withhold of study drug for > 28 days due to adverse event, unless approved by medical monitor.
- Development of an intercurrent illness, condition or procedural complication, which could interfere with the patient's continued participation.
- Voluntary patient withdrawal from study treatment (all patients are free to withdraw from participation in this study at any time, for any reasons, specified or unspecified, and without prejudice).
- Any other situation where, in the opinion of the investigator, continued participation in the study would not be in the best interest of the patient
- Confirmed disease progression
- Study completion.

## **5 TREATMENT OF SUBJECTS**

### **5.1 Administration of Tenalib**

Tenalib will be dosed continuously twice a day in 28-days cycle up to 24 months unless progression of disease or toxicity warranting discontinuation of therapy. Please refer [section 3.4.3](#) for administration of Tenalib. Post completion of 24 months, if the patient shows clinical benefit, patient may be enrolled into a compassionate use study protocol to receive Tenalib.

### **5.2 Concomitant Medications**

- Antimicrobial and anti-viral prophylaxis should be used according to local standard

practice; PCP and Zoster prophylaxis is strongly recommended.

- G-CSF and other hematopoietic growth factors may be used for the management of acute toxicity such as febrile neutropenia when clinically indicated.
- Transfusions (blood/platelets) may be given, based on standard criteria and clinical judgment.
- No routine prophylactic anti-emetics or pre-medications should be given outside of protocol requirements. However, these medications may be administered for the treatment of symptoms.
- Patient may receive prophylactic allopurinol, in case the risk of tumor lysis syndrome.
- Low doses of steroids are allowed if it stabilized at < 20 mg per day of prednisone or equivalent. If initiated before starting treatment, corticosteroid should be stabilized for at least 1 week prior to C1D1.
- Patients are permitted to use of topical, ocular, intra-articular, intranasal, and inhaled corticosteroids (with minimal systemic absorption). A brief (less than 3 weeks) course of corticosteroids for prophylaxis (e.g. contrast dye allergy) or for treatment of non-autoimmune conditions (e.g., delayed-type hypersensitivity reaction caused by a contact allergen) and also for the treatment of drug-related AE is permitted.
- Inactivated seasonal influenza vaccine can be given to subjects before treatment and while on therapy without restriction.
- If concomitant treatment of drugs metabolized by CYP3A4/CYP2C9 enzymes are clinically warranted, careful observation of the patient is advised. Use of heparin or warfarin for prophylaxis and treatment of venous thrombosis is prohibited. Low molecular weight heparin (LMWH) is acceptable. Similarly, Dabigatran and Edoxaban, Direct-acting Oral Anti-Coagulants (DOAC) class of drugs, are acceptable as they are not metabolized by CYP3A4/CYP2C9 enzymes.
- Patients should be warned about the possible photosensitivity and advised to be careful with the UV exposure while on Tenalisib treatment. Patients should be recommended to wear loose-fitting clothes that protect skin from sun exposure, in case they need to be outdoors. If sunburn like reaction or skin eruption occurs, patients should contact study physician.

### 5.3 Prohibited Medications

The following treatments are prohibited while on the clinical trial:

- Any other anti-lymphoma therapy (e.g. radiation therapy, hormonal therapy for cancer, cancer immunotherapy or other biologic therapy).
- Herbal medications are not allowed throughout the trial. Patients should stop using these herbal medications at least 7 days prior to C1D1.
- **Strong inhibitors or inducers of CYP3A4**, including grapefruit products, herbal medication (e.g. atazanavir, clarithromycin, indinavir, itraconazole, ketoconazole, nefazodone, nelfinavir, ritonavir, saquinavir, telithromycin and rifampicin). Patients should stop using these medications at least 7 days prior to C1D1.
- **Strong inhibitors or inducers of CYP2C9**, including herbal medications (e.g. fluconazole and rifampicin). Patients should stop using these medications at least 7 days prior to C1D1.
- **Substrates of CYP3A4 enzyme with a narrow therapeutic range** (e.g. Warfarin and

phenytoin, alfentanil, astemizole, cisapride, cyclosporine, diergotamine, ergotamine, fentanyl, pimozide, quinidine, sirolimus, tacrolimus, terfenadine). Patients should stop using these medications at least 7 days prior to C1D1.

- Use of heparin or warfarin for prophylaxis and treatment of venous thrombosis is prohibited. Similarly, Apixaban and Rivaroxaban, DOAC class of drugs, are also prohibited they are metabolized by CYP3A4 enzymes. These drugs should be stopped at least 7 days prior to C1D1. Live attenuated vaccine (e.g. Flu vaccine, pneumovax, varicella)
- Steroids > 20 mg unless for management of toxicity.

**Discontinuation of patient who received concomitant/prohibited medication will be taken by the PI in consultation with medical monitor on case to case basis, after reviewing ongoing clinical benefit and risk. The decision to allow a patient to continue will be documented and archived at the site and at Rhizen.**

#### **5.4 Procedures for Monitoring Subject Compliance.**

The following measures will be employed to ensure treatment compliance.

Subjects will be asked to bring any unused study drug to the research center at their next visit. Research personnel will count and record the number of used and unused study drug tablets at each visit. The study coordinator will question the patient regarding adherence to the dosing regimen, record the number of tablets and strengths returned, the date returned and determine treatment compliance before dispensing new medication to the study patient. Compliance below 80% will require counseling of the patient by study site personnel.

## **6 TRIAL ASSESSMENT AND PROCEDURE**

### **6.1 Overview**

Schedule of Event (**Table 1**) summarizes the trial procedures to be performed at each visit and is divided into following.

1. Screening (Day -28 day to Day 0)
2. On treatment procedures (C1D1 to C8D28)
3. Treatment beyond Cycle 9 (C9D1 to C26)
4. End of Treatment (Day +7 from last dose)
5. End of Study (Day +30 from last dose)

Individual trial procedures are described in detail below. It may be necessary to perform these procedures at unscheduled time points if deemed clinically necessary by the investigator.

Furthermore, additional evaluations/testing may be deemed necessary by the investigator and or the Sponsor for reasons related to subject safety. In some cases, such evaluation/testing may be potentially sensitive in nature (e.g., HIV, Hepatitis C, etc.), and thus local regulations may require that additional informed consent be obtained from the

[REDACTED]

subject. In these cases, such evaluations/testing will be performed in accordance with those regulations.

Table 1: Schedule of Events for Part 1															
	Screening	Cycle 1		Cycle 2		Cycle 3		C4	C5	C6	C7	C8	C9-26	EOT 	EOS 
Day	D-28 to 0	D1	D15	D1	D15	D1	D15	D1	D1	D1	D1	D1	D1	-	-
Window period	-28	±1	±1	±1	±3	±3	±3	±3	±7	±7	±7	±7	±7	+14	+30
Study Days	D-28 to 0	1	15	29	43	57	71	85	113	141	169	197	-	-	-
Informed Consent 	X	-	-	-	-	-	-	-	-	-	-	-	-	-	-
Demographics 	X	-	-	-	-	-	-	-	-	-	-	-	-	-	-
Medical history 	X	-	-	-	-	-	-	-	-	-	-	-	-	-	-
Vitals 	X	X	X	X	X	X	X	X	X	X	X	X	-	X	-
Height and weight 	X	X	X	X	X	X	X	X	X	X	X	X	-	X	-
Complete Physical exam 	X	-	-	-	-	-	-	-	-	-	-	-	-	X	-
Abbreviated Physical exam 	-	X	X	X	X	X	X	X	X	X	X	X	-	-	-
ECOG Performance Status	X	X	-	-	-	X	-	-	X	X	X	X	-	X	-
Complete blood count 	X	X	X	X	X	X	X	X	X	X	X	X	X 	X	-
Chemistry panel I 	X	X	X	X	X	X	X	X	X	X	X	X	X 	X	-
Chemistry panel II 	X	X	-	-	-	X	-	-	X	-	-	X	-	X	-
Serology 	X	-	-	-	-	-	-	-	-	-	-	-	-	-	-
PT and INR 	X	X	X	X	X	X	X	X	X	X	X	X	-	X	-
Urinalysis (routine)	X	X	X	X	X	X	X	X	X	X	X	X	X 	X	-
Pregnancy test 	X	X	X	X	X	X	X	X	X	X	X	X	-	X	-
12-lead ECGs 	X	X	X	X	X	X	X	X	-	-	-	X	-	X	-
Radiological scan/imaging	X	-	-	-	-	X	-	-	X	-	-	X	X 	X	-
CT scan 	X	-	-	-	-	-	-	-	X	-	-	X	X 	X	-
PET/PET-CT 	X	-	-	-	-	X	-	-	-	-	-	-	-	-	-
Disease Response Assessment 	X	-	-	-	-	X	-	-	X	-	-	X	X 	X	-
Drug Dispensing 	-	X	-	X	-	X	-	X	X	X	X	X	X 	X	-

Tenalisib treatment 	-	X	X	X	X	X	X	X	X	X	X	X	X 	X	-
Drug compliance	-	-	X	X	X	X	X	X	X	X	X	X	-	X	-
AE evaluation 	X	X	X	X	X	X	X	X	X	X	X	X	X 	X	X
SAE evaluation	X	X	X	X	X	X	X	X	X	X	X	X	X 	X	X
Concomitant medication	-	X	X	X	X	X	X	X	X	X	X	X	X 	X	X

**Foot notes:**

1. Patient should be re-consented, if informed consent is obtained >30 days prior to the initiation of trial treatment. The first day of Tenalisib administration will be considered as C1D1.
2. Demographic profile will include age, sex and race.
3. Detailed history will be taken at screening that includes history of cancer, past history, number of prior therapies; and prior medication (in last 4 weeks); and other medical history. Any medical significant history at subsequent visit will be captured as adverse event.
4. Vitals will include pulse; blood pressure; respiratory rate and oral temperature that should be done at screening, C1D1 (within 30 minutes prior to dosing) and at the time of clinic visit at all other time points. Supine or sitting position is acceptable depending on the patient condition.
5. Weight will be measured at all visits. Height to be measured at screening only.
6. Physical examination will include lymph node and systemic examination (General Appearance, HEENT, neck, cardiovascular, lungs, abdomen, lymph nodes, genitourinary, extremities, neurological, skin, and musculoskeletal). Complete physical examination will be done at screening visit and EOT. At all other visits, abbreviated examination (directed physical examination) will be done depending on the assessment of tumor.
7. This will include hemoglobin, complete blood count, total leucocyte and differential count and platelet count. Additional investigations will be performed if clinically indicated. Hematology must be done ≤7 days prior to C1D1. However, if these initial examinations are obtained within 72 hours of C1D1; they do not have to be repeated.
8. Chemistry Panel I includes total bilirubin, ALP, AST, ALT, GGT, LDH, sodium, potassium, chloride, calcium, phosphorus, CO2/bicarbonate and magnesium. These tests must be done ≤7 days prior to C1D1. However, if these initial examinations are obtained within 72 hours of C1D1; they do not have to be repeated. These tests will be performed at supplementary visits if clinically indicated.
9. Chemistry Panel II includes blood glucose, urea/ blood urea nitrogen (BUN), creatinine, albumin, total protein, TSH, T3 (total/free), T4 (free), total Cholesterol, TG, LDL and HDL. These tests must be done ≤7 days prior to C1D1. However, if these initial examinations are obtained within 72 hours of C1D1; they do not have to be repeated. These tests will be performed at supplementary (unscheduled) visits if clinically indicated.
10. Serology includes HIV, HBV and HCV. Historical evidence in the last 4 weeks is acceptable.
11. PT and INR test must be done ≤7 days prior to C1D1. However, if initial examination is obtained within 72 hours of C1D1; this do not have to be repeated. In case of abnormality, additional tests including aPTT to be done as per investigator discretion. This test will be performed at supplementary visits if clinically indicated.
12. This is required for women of child bearing potential. A serum pregnancy test will be performed at screening and C1D1 (within 72 hours) of dosing. Urine pregnancy test will be performed at other visits as indicated.
13. A standard 12-lead ECG will be performed at the defined time points. Additional ECGs will be obtained if clinically indicated. Triplicate ECGs will be performed to confirm significant changes of a single ECG.

14. PET/PET-CT and “diagnostic quality” CT scan will be performed at the time of screening within 28 days of screening. Following screening, CT scans should be repeated at C5D1 and at every 12-Weeks thereafter. PET/PET-CT should be repeated at C3D1 and to confirm CR/PD; and as clinically indicated. Tumor imaging should remain consistent throughout study, and should include those thought by investigator to best capture the status of disease. Baseline scans if already available as SOC within 28-days of screening, is accepted as part of study protocol.
15. Disease response assessment will be performed at C3D1 ( $\pm$  7 days), C5D1 ( $\pm$  7 days) and approximately every 12 weeks thereafter ( $\pm$  7 days), and/ or at the EOT or as clinically indicated (if clinical progression is suspected or for confirmation of complete response/disease progression) using Cheson Criteria 2014.
16. Tenalisisib will be dispensed in a HDPE container having 30 tablets of Tenalisisib.
17. Tenalisisib will be administered orally twice a day in 28-days of cycle in absence of disease progression or toxicity warranting discontinuation of therapy. Post cycle 8, Tenalisisib will be continued in patients experiencing clinical benefit up to 24 months unless progression of disease or toxicity warranting discontinuation of therapy. The decision to continue the treatment will be taken by PI after consultation with Sponsor on case to case basis.
18. All AEs regardless of seriousness or relationship to study drug should be recorded spanning from the informed consent drug until 30 calendar days after the last dose of study drug.
19. Post cycle 8, all visits will occur monthly. During these monthly visits, Tenalisisib will be dispensed, medication compliance will be monitored. Safety and efficacy assessments will be done as mentioned below. An EOT visit will be performed within 14 days after treatment ends.
  - Safety assessments: Safety assessment will be done during the monthly visits and AEs will be reported as required by the protocol. There is no specific safety labs or evaluations to be done as per protocol. As part Standard of care, laboratory evaluations will be done and recorded per Investigator’s discretion. Adverse events (AEs, SAEs and deaths) will be recorded and reported for 30 calendar days after discontinuation or completion of protocol-specific treatment. After the 30 day reporting period, only AEs, SAEs, or deaths assessed by the investigator as treatment related are to be reported.
  - Efficacy assessments: Disease assessments should be performed at 12 weekly intervals ( $\pm$  7 days), and/ or at the EOT. For example, the appropriate radiological investigation (e.g. CT scan, PET-CT/PET) will be performed patients at C11D1, C14D1, C17D1, C20D1, etc.
  - Drug dispensing: Patients will be given 30 days of drug supply at the beginning of each cycle.
20. All patients will undergo the end-of-treatment (EOT) assessments within 14 days after last dose of study drug or discontinuation.
21. Patients should be followed for AEs for 30 calendar days after the last dose of study treatment. Telephonic follow up during this period is acceptable. All new AEs occurring during this period should be reported and followed until resolution unless, in the opinion of the investigator, the adverse event or laboratory abnormality/ies are not likely to improve because of the underlying disease.

## **6.2 Screening and on Treatment Procedures**

### **6.2.1 Informed consent**

The investigator/qualified designee must obtain documented consent from each potential subject or each subject's legally acceptable representative prior to participating in a clinical trial. Consent must be documented by the subject's dated signature or by the subject's legally acceptable representative's dated signature on a consent form along with the dated signature of the person conducting the consent discussion. A copy of the signed and dated consent form should be given to the subject before participation in the trial.

The initial informed consent form, any subsequent revised written informed consent form and any written information provided to the subject must receive the IRB/IEC's approval/favorable opinion in advance of use. The subject or his/her legally acceptable representative should be informed in a timely manner if new information becomes available that may be relevant to the subject's willingness to continue participation in the trial. The communication of this information will be provided and documented via a revised consent form or addendum to the original consent form that captures the subject's dated signature or by the subject's legally acceptable representative's dated signature. Specifics about a trial and the trial population will be added to the consent form template at the protocol level. The informed consent will adhere to IRB/IEC requirements, applicable laws and regulations and Sponsor requirements.

The informed consent must be obtained  $\leq 30$  days prior to initiation of treatment before any protocol-specific procedures are performed. Patient should be re-consented in case informed consent is not obtained  $\leq 30$  days prior to the initiation of trial treatment.

### **6.2.2 Assignment of screening number**

All consented subjects who undergo at least one post-consent procedure will be given a unique screening number that will be used to identify the subject for all procedures that occur prior to randomization or allocation. Each subject will be assigned only one screening number. Screening numbers must not be re-used for different subjects. Any subject who is screened multiple times will retain the original screening number assigned at the initial screening visit.

### **6.2.3 Medical history**

A medical history will be obtained by the investigator/qualified designee. Comprehensive history will include but not limited to age; sex; absence/presence of fever more than 101°F (38.3°C), chills, drenching night sweats, or unexplained weight loss more than 10% of body mass over 6 months; and history of malignancy. Medical history should be taken for period of minimum 6 months.

### **6.2.4 Prior and concomitant medication review**

**Prior medication:** The investigator/qualified designee will review prior medication use, including any protocol-specified washout requirement, and record prior medication taken by the subject within 28 days before starting the trial. Treatment for the disease for which the subject has enrolled in the study will be recorded separately and not listed as a prior medication.

**Concomitant medication:** The investigator/qualified designee will record medication, if any, taken by the subject during the trial.

### 6.2.5 Prior therapies details

The investigator/qualified designee will review all prior cancer treatments including systemic treatments, prior transplantation, radiation, and surgeries received for the treatment of cancer condition from the initial diagnosis and record in the source document.

### 6.2.6 Physical examination

**Full physical examination:** The investigator/qualified designee will perform a complete physical exam during the screening period and as defined in Schedule of Events. Physical examination will include lymph node and systemic examination (General Appearance, HEENT, neck, cardiovascular, lungs, abdomen, lymph nodes, genitourinary, extremities, neurological, skin, and musculoskeletal).

**Abbreviated (Directed) physical examination:** For cycles that do not require a full physical exam per the Schedule of Event, the investigator/qualified designee will perform a directed physical exam as clinically indicated depending on assessment of tumor, prior to trial treatment administration. After the first dose of trial treatment new clinically significant abnormal findings should be recorded as AEs.

### 6.2.7 Vital signs

Vital signs will be taken at screening, C1D1 (within 30 minutes prior to dosing) and at the time of clinic visit at all other time points as specified in the Schedule of Event. Vital signs should include temperature (oral/axillary), pulse, respiratory rate, weight and blood pressure. Supine or sitting position is acceptable depending on the patient condition. The window periods for vitals will  $\pm 30$  min for the specified time points.

### 6.2.8 Laboratory safety evaluations

Laboratory tests for hematology, chemistry and urinalysis are specified in **Table 2**.

**Table 2: Laboratory Tests for Hematology, Chemistry and Urinalysis**

Hematology	Chemistry Panel I	Chemistry Panel II	Urinalysis	Other
Hematocrit	Total bilirubin	Blood glucose	Blood	Serum $\beta$ -hCG
Hemoglobin	Alkaline phosphatase (ALP)	Urea or blood urea nitrogen a	Glucose	Urine pregnancy test
CBC with differentials	Alanine aminotransferase (ALT)	Creatinine	Protein	PT
Platelet count	Aspartate aminotransferase (AST)	Albumin	Specific gravity	INR
WBC (Total and differentials)	Lactate dehydrogenase (LDH)	Total protein	Microscopic exam	
Red blood cell count	Gamma-glutamyl transferase (GGT)	Total Cholesterol		
Absolute neutrophil count	Sodium	Triglyceride (TG)		
Absolute lymphocyte count	Potassium	LDL		

	Calcium	HDL		
	Phosphorous	TSH		
	Carbon Dioxide (CO 2 ) or bicarbonate C	T3 (Total or Free) d		
	Chloride	T4 (free)		
	Magnesium			

a Blood Urea Nitrogen is preferred; if not available Urea may be tested.

b Microscopic exam, if abnormal results are noted.

c One of these tests to be performed depending on standard of care practice followed at the institution.

d Free or total T3 to be performed depending on standard of care practice followed at the institution.

Blood drawn for these tests will be specified in informed consent form (ICF). The investigations will be performed at the local laboratory as decided by the sponsor and investigator. .

Screening laboratory described in **Table 2** will be performed, reviewed, and determined to be acceptable by the site PI/designee after obtaining informed consent and ≤7 calendar days prior to the initiation of treatment. If these initial examinations are obtained within 72 hours (or as otherwise noted) of Cycle 1 Day 1, the investigations need not be repeated. Rescreening can be done at the discretion of PI. The scan and other investigations to document measurable or evaluable disease should be performed ≤28 weeks prior to initiation of treatment.

During screening, active HBV, HCV or HIV infection should be ruled out. To be considered negative for active infection, following algorithm will be used:

- HBV: HBc antibody should be negative or if HBc antibody is positive, HBVDNA should be undetectable
- HCV: HCV antibody should be negative or if HCV antibody is positive, HCVDNA should be undetectable
- HIV: HIV antibody should be negative. (HIV 1/ 2 antibody should be negative unless positive result is considered false positive by PI)

***Note:** Patients who show evidence of hepatitis B infection (HBsAg positive [regardless of antibody status] or HBsAg negative but anti-HBc positive), need to be evaluated for initiation of HBV antiviral therapy and should be closely monitored for HBV reactivation.*

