
Exclusion Criteria
	
 
1. Histologically confirmed diagnosis of follicular lymphoma grade 3b or transformed disease or chronic lymphocytic leukemia (CLL).
 
2. Patients receiving cancer therapy (i.e., chemotherapy, radiation therapy, immunotherapy, biologic therapy, hormonal therapy, surgery and/or tumor embolization) or any cancer investigational drug within 3 weeks (21 days) or 5 half-lives (whichever is shorter) prior to C1D1. Corticosteroids (prednisone or equivalent) at a dose of <math>< 20</math> mg daily are allowed. Corticosteroid should be stabilized for at least 1 week prior to C1D1.
 
3. Autologous hematologic stem cell transplant (Auto-SCT) within 3 months from C1D1. Patients must not have active graft versus-host disease;
 
4. History of an allogeneic bone marrow transplant (Allo-SCT)
 
5. Active hepatitis B or C infection. (All subjects must be screened for hepatitis B and C up to 28 days prior to C1D1 using the hepatitis viral panel. Subject positive for HBsAg or HBcAb will be eligible if they are negative for HBV-DNA. Subject positive for HCV IgG will be eligible if they are negative for HCV-RNA);
 
6. Known history of human immunodeficiency virus (HIV) infection;
 
7. Evidence of ongoing severe systemic bacterial, fungal or viral infection;
 
8. Known primary central nervous system lymphoma or known intracranial involvement, leptomeningeal metastases or spinal cord compression due to disease or any preexisting neurologic manifestations;
 
9. Known history of severe drug-induced liver injury; alcoholic liver disease, primary biliary cirrhosis, ongoing extrahepatic obstruction caused by stones, cirrhosis of the liver or portal hypertension;
 
10. Patient with any severe and/or uncontrolled medical conditions or other conditions that could affect their participation in the study as per investigator's judgment;
 
11. Patient with symptomatic or history of documented congestive heart failure (NY Heart Association functional classification III-IV).
 
12. Patient with angina not well-controlled by medication
 

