#### **6.6 Treatment Beyond Cycle 8 (Cycle 9 onward up to Cycle 26)**

Post cycle 8, all visits will occur monthly in responding patients. During these monthly visits, Tenalisib will be dispensed, medication compliance will be monitored. Safety and efficacy assessments will be done as mentioned below. An EOT visit will be performed within 14 days after treatment ends.

- **Safety assessments:** Safety assessment will be done during the monthly visits and AEs will be reported as required by the protocol. There is no specific safety labs or evaluations to be done as per protocol. As part Standard of care, laboratory evaluations will be done and recorded per Investigator's discretion. Adverse events (AEs, SAEs and deaths) will be recorded and reported for 30 calendar days after discontinuation or completion of protocol-specific treatment. After the 30 day reporting period, only AEs, SAEs, or deaths assessed by the investigator as treatment related are to be reported.
- **Efficacy assessments:** Disease assessments should be performed at 12 weekly intervals ( $\pm$  7 days), and/ or at the EOT. For example, the appropriate radiological investigation (e.g. CT scan, PET-CT/ PET) will be performed patients at C11D1, C14D1, C17D1, C20D1, etc.
- **Drug dispensing:** Patients will be given 30 days of drug supply at the beginning of each cycle.

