**Table 4: Dose Modifications for Non-Hematologic Toxicities**

NON-HEMATOLOGIC	Action to be Taken
Renal*	If serum creatinine Grade ≥3 (>3 x baseline or >3 x ULN), hold dose until ≤ grade 2. Monitor serum creatinine at least twice a week until resolution to ≤ grade 2, and then at least one week until it resolves to ≤ grade 1.
Hepatic*	
Transaminitis
 
Grade ≥ 1 Transaminitis (ALT/AST > 1-3 X ULN):
 
 
• Maintain Tenalisib dose and initiate prednisone 40 mg daily.
 
• Monitor AST/ALT weekly until resolved.
 
• Withhold Tenalisib in case of development of grade 2 transaminitis or worsening of Grade 1 transaminitis while on steroids.
 
 
Grade ≥ 3 Transaminitis (ALT/AST >5–20 X ULN):
 
 
• Withhold Tenalisib and monitor ALT/AST twice a weekly until Grade ≤1; restart Tenalisib at 400 mg BID dose level.
 
• Initiate prednisone 1 mg/kg in case no improvement with discontinuation of Tenalisib in 1 week.
 
• Monitor ALT/AST twice a weekly until Grade ≤1; restart Tenalisib at 400 mg BID dose level and taper steroid.
 
• If no immediate response to steroids within 7 days, initiate mycophenolate mofetil.
 
• In case of recurrence of transaminitis at reduced doses, discontinue Tenalisib permanently after assessing risk versus benefit.
 
 
Grade ≥ 4 Transaminitis (ALT/AST >20 X ULN):
 
 
• Tenalisib should be permanently discontinued.
 

	
Bilirubin:
 
 
• Grade <math>\geq 2</math> (<math>> 1.5-3 \times \text{ULN}</math>): Maintain Tenalisib dose. Monitor at least weekly until <math>\leq 1 \times \text{ULN}</math>
 
• Grade <math>\geq 3</math> (<math>> 3-10 \times \text{ULN}</math>): Withhold Tenalisib. Monitor at least weekly until bilirubin is <math>\leq 1 \times \text{ULN}</math>; restart Tenalisib at 400 mg BID dose level.
 
• Grade <math>\geq 4</math> (<math>> 10 \times \text{ULN}</math>): Discontinue Tenalisib permanently
 

Infection	
Grade 3 or higher sepsis or pneumonia
 
 
• Interrupt Tenalisib until infection has resolved.
 

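### Patients admitted with hepatitis B markers but negative HBV-DNA can be started on prednisone, and later mycophenolate, for a transaminase rise without an HBV-DNA check, and no HBV test is scheduled after screening

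*Protocol*

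**What the plan says.** **Entry.** Exclusion criterion 5 (Synopsis and section 4.2) states: "Subject positive for HBsAg or HBcAb will be eligible if they are negative for HBV-DNA". The screening algorithm in 6.2.8 uses the same test: "HBc antibody should be negative or if HBc antibody is positive, HBVDNA should be undetectable".

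**Monitoring.** The Note closing 6.2.8 says that patients with evidence of hepatitis B infection "need to be evaluated for initiation of HBV antiviral therapy and should be closely monitored for HBV reactivation". It gives no test, interval or action.

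**Schedule.** Table 1 marks serology at screening only. Its footnote 10 reads: "Serology includes HIV, HBV and HCV. Historical evidence in the last 4 weeks is acceptable". Chemistry Panel I, which contains ALT and AST, is marked at every visit to C8D1, under footnote 19 for cycles 9-26, and at EOT. For cycles 9-26, section 6.6 sets no protocol-specific safety labs: "As part Standard of care, laboratory evaluations will be done and recorded per" the investigator's discretion.

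**Response to raised transaminases (Table 4, Hepatic).**
- Grade ≥1 (above 1 to 3 × ULN): "Maintain Tenalisib dose and initiate" prednisone 40 mg daily. AST/ALT are then checked weekly, and Tenalisib is withheld if Grade 2 develops or Grade 1 worsens on steroids.
- Grade ≥3 (above 5 to 20 × ULN): Tenalisib is withheld with twice-weekly ALT/AST. Prednisone 1 mg/kg is given "in case no improvement with discontinuation of Tenalisib in 1 week". Then: "If no immediate response to steroids within 7 days, initiate mycophenolate mofetil".
- Grade 4 (above 20 × ULN): permanent discontinuation, with no steroid named.

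**Attribution.** Section 7.6.2 applies the table to events that the investigator judges related. Section 7.2 presumes relatedness unless there is a clear alternative explanation, and allows a judgement of not related when another cause is found.

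**The concern.** The protocol itself treats HBV reactivation as something to watch for in these patients. The only routine laboratory signal it schedules that could point to reactivation is ALT/AST, and that is the same signal that starts prednisone in Table 4. A patient whose rise is in fact reactivation would meet the steroid rule before anyone has been told to look for virus. The event could also be recorded as related to Tenalisib, because the cause that would rebut the default in 7.2 can be identified only by a test left to discretion.

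What is at stake is the safety of individual patients and the attribution of individual events. The documents do not state the clinical hazard of immunosuppression during reactivation. That hazard is a premise here, for the sponsor's clinicians to weigh. The gap between the Note and the two tables can be shown from the text alone.

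**Working it through.** The plan gives no figure on this point to reproduce. The check is a reading of the sections against each other, with two counts.

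**1. Are these patients in the trial population?** Yes. Exclusion criterion 5 admits them, and the Note addresses HBsAg-positive patients and HBsAg-negative, anti-HBc-positive patients by name.

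**2. What is tested after screening?** Table 1 has 15 columns: screening, then C1D1, C1D15, C2D1, C2D15, C3D1, C3D15, C4, C5, C6, C7, C8, C9-26, EOT and EOS.
- Serology: 1 of 15 (screening), so 0 of the 14 later columns.
- ALT/AST after C1D1: 10 visits to C8D1 + C9-26 (footnote 19) + EOT = 12 of 13 columns; EOS is not marked.
- Table 2 lists no HBV test. The SAP's listings (section 12) include baseline serology only.

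An ALT/AST rise will therefore usually be seen up to cycle 8. After that, detection depends on discretionary labs. The virus itself is never scheduled to be looked for.

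**3. What follows a rise?** Steps in the hepatic row of Table 4 that ask for HBV-DNA, or that treat HBV-positive entrants separately: 0.
- Grade ≥1: prednisone at once, with Tenalisib continued.
- Grade ≥3: 7 days off Tenalisib without improvement, then prednisone; 7 days without steroid response, then mycophenolate. 7 + 7 = 14 days from hold to mycophenolate.

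**4. Does another provision put a test before the steroid?**
- Weekly AST/ALT and the hold on worsening (Grade ≥1 branch): these act after prednisone has started. They stop Tenalisib and do not ask for the cause.
- Section 6.1: allows unscheduled and additional tests but requires none.
- Section 7.2, not related: available only once another cause is identified, and no HBV test is prescribed to identify it.
- Section 5.2: anti-viral prophylaxis by local practice. HBV is not named and no test is set.
- Antiviral evaluation in the 6.2.8 Note: may lead to treatment but sets no on-treatment test.
- Section 7.6 and the footnotes to the dose tables: medical monitor discussion when drug is delayed more than 2 weeks for an adverse event. That falls at or after the 14-day mycophenolate step, and it does not arise in the Grade ≥1 branch while Tenalisib continues.
- Section 12.3 (regular medical monitor review of AEs) and section 3.7 (DRC about every 3 months): neither is timed to the decision to start a steroid.

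Each of these lowers the risk. None supplies the missing step.

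**5. How low is the threshold?** Inclusion criterion 7e allows entry with ALT/AST up to 1.5 × ULN, or 2.5 × ULN with liver involvement. Both limits lie inside the Table 4 band of above 1 to 3 × ULN. A workable trigger must therefore refer to new or worsening values, not to any raised value.

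**The case against.** The strongest reply is that the protocol leaves detail out but does not contradict itself. The Note already singles out these patients. Table 4 applies only to events judged related, and an investigator who follows the Note would think of HBV before judging. Testing is allowed at any time. The Grade ≥1 branch has weekly AST/ALT and a hold on worsening, and a prolonged delay brings in the medical monitor. Section 3.5.5 refers to an Investigator's Brochure that is not available here. The study is closed.

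Much of this stands. The Note says should, so it is fair to call the monitoring recommended but not mandated. A reader might infer that Table 4 obliges steroids in a patient with known reactivation. It does not, because a known cause takes the event outside 7.6.2. A reader might also infer that a rise would go unseen; up to cycle 8 that is wrong. What remains is that Table 4 gives a positive instruction to immunosuppress, triggered by the signal that reactivation would give, with no prompt to look first.

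A reader might also try to put a rate on this from section 1.1.2. It lists treatment-related Grade ≥3 AST/ALT elevation with n = 11 of 49 (22.4%) in RP6530-1401 and none among 35 in RP6530-1301; pooled, 11/84 = 13.1%, or 2.6 of 20. The documents do not support that figure as the size of this problem. The two studies differ clearly (Fisher exact p = 0.002), in different diseases and at different doses. Whether n counts patients is not stated. The figure also describes all entrants, not those with HBV markers. If, purely as an assumption, 5 to 20% of 20 patients were HBV-positive, the two study rates would give from 20 × 0.05 × 0 = 0 to 20 × 0.20 × 0.224 = 0.9 patients at Grade ≥3, before asking whether any such event was HBV. For Grade ≥1 the documents give no rate.

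**Conclusion.** The point holds as a gap in the safety procedures for one subgroup. The protocol admits patients with HBV markers and negative HBV-DNA and says they should be closely monitored for reactivation. It schedules no HBV test in any of the 14 columns after screening, and it starts prednisone, and at Grade ≥3 possibly mycophenolate, without an HBV-DNA check. The existing safeguards reduce the risk but do not put a test ahead of immunosuppression.

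The size cannot be given. The number of HBV-positive entrants is not reported and may be zero, and no figure in the documents measures reactivation. No efficacy or safety estimate is claimed to change, and nothing shows that a patient was harmed. The SAP (section 5.1, Notes) reports the study closed and Part 2 not performed. The point therefore applies to any patients still treated under this text and to a successor, such as the compassionate use protocol foreseen in protocol section 5.1. It rests on the clinical premise that reactivation should be excluded before immunosuppression is added.

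**What to change.** For patients admitted as HBsAg- or HBcAb-positive with negative HBV-DNA only:

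1. **Table 4, Hepatic (main change).** At new or worsening transaminitis that meets a Table 4 grade (above the patient's baseline if that was raised), draw HBV-DNA before assigning relatedness and before starting prednisone or mycophenolate. Any Tenalisib hold that the table calls for goes ahead without waiting for the result.
2. **6.2.8 Note and Table 1 (supporting change).** Name HBV-DNA as the monitoring test and add a conditional row to Table 1 that includes cycles 9-26, where labs are otherwise discretionary. The interval, and the management of a positive result, are for the sponsor's clinicians.

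The cost is one sentence in Table 4, one in the Note and one conditional row. The test is already used to establish these patients' eligibility. The downside is a small laboratory cost and a short wait for steroids. At Grade ≥3 the test can run inside the 1-week window that Table 4 already has, so the wait falls mainly on the Grade 1 branch. The documents give no turnaround time, so the length of that wait should be settled with the sites.
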